## 4.2 Exclusion Criteria

Patients who meet any of the following criteria will be excluded from the study. Study treatment is defined as defibrotide prophylaxis in addition to BSC or BSC alone.

1. Patient has hemodynamic instability within 24 hours before the start of study treatment.
2. Patient has acute bleeding that is clinically significant within 24 hours before the start of study treatment, defined as either of the following (a or b):
  - a. hemorrhage requiring >15 cc/kg of packed red blood cells (e.g., pediatric patient weighing 20 kg and requiring 300 cc packed red blood cells/24 hours, or an adult weighing >70 kg and requiring 3 units of packed red blood cells/24 hours) to replace blood loss, or
  - b. bleeding from a site which, in the investigator's opinion, constitutes a potential life-threatening source (e.g., pulmonary hemorrhage or central nervous system bleeding), irrespective of amount of blood loss
3. Patient used any medication that increases the risk of bleeding within 24 hours before the start of study treatment, including, but not limited to, systemic heparin, low molecular weight heparin, heparin analogs, alteplase (tPA), streptokinase, urokinase, antithrombin III (ATIII), and oral anticoagulants including warfarin, and other agents that increase the risk of bleeding. Patients may receive heparin or other anticoagulants for routine central venous line management and intermittent dialysis or ultrafiltration. Fibrinolytic instillation for central venous line occlusion is also permitted.  
Note: Heparin use will be allowed in both treatment arms (up to a maximum of 100 U/kg/day).
4. Patient is using or plans to use an investigational agent for the prevention or treatment of VOD.
5. Patient, in the opinion of the investigator, may not be able to comply with the safety monitoring requirements of the study.
6. Patient or parent/legal guardian or representative has a psychiatric illness that would prevent the patient or parent/legal guardian or representative from giving informed consent and/or assent.
7. Patient has a serious active disease or co-morbid medical condition, as judged by the investigator, which would interfere with the conduct of this study.

Defibrotide (JZP-381)  
Clinical Trial Protocol: 15-007 Version 4.0

Jazz Pharmaceuticals, Inc.  
20 August 2018

8. Patient is pregnant or lactating and does not agree to stop breastfeeding.
9. Patient has a known history of hypersensitivity to defibrotide or any of the excipients.
10. Patient or parent/legal guardian or representative lacks the full mental capacity to understand and sign a written informed consent.
11. Patient is receiving or plans to receive other investigational therapy during study.

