--	--

	
iv. Class III, high-risk thalassemia (i.e., patients who are <math>\geq 7</math> years old and have confirmed diagnosis of hepatomegaly (e.g., a liver size <math>\geq 5</math> cm below the costal margin on clinical examination) at the time of screening [Mathews et al. 2007])
 
3. Female patients (and female partners of male patients) of childbearing potential who are sexually active must agree to use a highly effective method of contraception with their partners during exposure to defibrotide and for 1 week after the last dose of defibrotide. Highly effective methods of contraception that may be used by the patient or partner include abstinence (when this is in line with the preferred and usual lifestyle of the patient [periodic abstinence, e.g., calendar, post-ovulation, symptothermal methods, and withdrawal are not acceptable methods]), combined (estrogen- and progestogen-containing) hormonal contraception associated with inhibition of ovulation (i.e., birth control pills, patches, vaginal ring), progestogen-only hormonal contraception associated with inhibition of ovulation (i.e., progestin implant or injection), intrauterine device (IUD), intrauterine hormone-releasing system (IUS), surgical sterilization, and vasectomy (>6 months before Study Day 1). Post-menopausal women (i.e., women with >2 years of amenorrhea) do not need to use contraception.
 
4. Adult patients must be able to understand and sign a written informed consent. For minor patients, the parent/legal guardian or representative must be able to understand and sign a written informed consent. Assent, when appropriate, will be obtained according to institutional guidelines.
 
Patients who meet any of the following criteria will be excluded from the study. Study treatment is defined as defibrotide prophylaxis in addition to BSC or BSC alone.
 
 
1. Patient has hemodynamic instability within 24 hours before the start of study treatment.
 
2. Patient has acute bleeding that is clinically significant within 24 hours before the start of study treatment, defined as either of the following (a or b):       
 
a. Hemorrhage requiring >15 cc/kg of packed red blood cells (e.g., pediatric patient weighing 20 kg and requiring 300 cc packed red blood cells/24 hours, or an adult weighing >70 kg and requiring 3 units of packed red blood cells/24hours) to replace blood loss, or
 
b. Bleeding from a site which, in the investigator's opinion, constitutes a potential life-threatening source (e.g., pulmonary hemorrhage or central nervous system bleeding), irrespective of amount of blood loss
 
 
 
3. Patient used any medication that increases the risk of bleeding within 24 hours before the start of study treatment, including, but not limited to, systemic heparin, low molecular weight heparin, heparin analogs, alteplase (tPA), streptokinase, urokinase, antithrombin III (ATIII), oral anticoagulants including warfarin, and other agents that increase the risk of bleeding. Patients may receive heparin or other anticoagulants for routine central venous line management, and intermittent dialysis or ultrafiltration. Fibrinolytic instillation for central venous line occlusion is also permitted. Note: Heparin use will be allowed in both treatment arms (up to 100 U/kg/day).
 
4. Patient is using or plans to use an investigational agent for the prevention or treatment of VOD.
 
5. Patient, in the opinion of the investigator, may not be able to comply with
 

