#### 5.2.1.2 Defibrotide Rescue Treatment for Patients who Develop VOD

For patients who develop VOD per modified Seattle criteria in either the DP or BSC arms, defibrotide will be administered as treatment for VOD until resolution of VOD or hospital discharge, whichever is sooner, and may continue beyond Day +30 post-HSCT. Patients must be hemodynamically stable and not at risk of bleeding, as defined in the first 3 exclusion criteria (#1, #2, #3) listed in [Section 4.2](#), to receive defibrotide as rescue treatment for VOD. Patients with VOD undergoing rescue treatment with defibrotide will continue to receive individualized standard of care therapy (BSC) based on local institutional guidelines and patient need. Medications that increase risk of bleeding must be stopped 24 hours prior to the start of defibrotide rescue treatment (see [Section 5.7.6](#)).

Defibrotide administration must be stopped if a patient has clinically significant bleeding. Defibrotide may be re-initiated if the bleeding is controlled and is of severity  $\leq$  grade 1.

The daily dose of defibrotide in patients who receive rescue treatment with defibrotide after being randomized to the DP or BSC arm will be based on body weight at baseline (i.e., within 24 hours before conditioning begins for the DP arm, and on the day that conditioning begins for patients in the BSC arm who develop VOD and subsequently receive defibrotide).

Defibrotide (JZP-381)  
Clinical Trial Protocol: 15-007 Version 4.0

Jazz Pharmaceuticals, Inc.  
20 August 2018

---

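### Bleeding exclusion 2a sets a limit of more than 15 cc/kg, but its child example only equals that limit and its adult example cannot match a per-kg rule; rescue eligibility reuses the criterion

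*Protocol*

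**What the plan says.** Exclusion criterion 2 in Protocol Section 4.2 concerns clinically significant acute bleeding in the 24 hours before study treatment starts. Part a defines it by transfusion volume per kilogram, with a child as the first example: "hemorrhage requiring >15 cc/kg of packed red blood cells (e.g., pediatric patient weighing 20 kg and requiring 300 cc packed red blood cells/24 hours". An adult example follows in the same parenthesis: "an adult weighing >70 kg and requiring 3 units of packed red blood cells/24 hours".

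Part b is a separate route to exclusion, based on a potentially life-threatening bleeding site whatever the volume lost.

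The synopsis carries the same rule, "Hemorrhage requiring >15 cc/kg of packed red blood cells", with the same two examples. Neither place gives a volume per unit or an upper weight for the adult example.

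Section 5.2.1.2 applies the criterion a second time, before rescue defibrotide: "Patients must be hemodynamically stable and not at risk of bleeding, as defined in the first 3 exclusion criteria" of Section 4.2.

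**The concern.** An example clarifies a rule only if it satisfies the rule. Here a site that computes cc/kg and a site that matches its patient to the printed examples can reach opposite answers under 2a for the same patient.

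This is the protocol's only volume threshold for bleeding. Section 1.6 lists bleeding first among the potential risks of defibrotide. About 100 sites are planned, and Section 1.5 expects most high-risk patients to be adults, so the adult example will be read often. Because rescue eligibility points back to the same criterion, an inconsistency at entry recurs when VOD is diagnosed. What is at stake is consistent eligibility on a safety criterion.

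**Working it through.** **Inputs.** From Protocol Section 4.2, criterion 2a (same in the synopsis): a limit of more than 15 cc/kg, as a strict inequality; a child of 20 kg receiving 300 cc in 24 hours; an adult above 70 kg receiving 3 units in 24 hours. The volume per unit, V, is not in either document. It is treated as unknown and varied from 200 to 500 cc.

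**Step 1: child example.** Volume / weight = 300 cc / 20 kg = 15.0 cc/kg. The rule needs more than 15, so the example ties with the limit and does not meet it. No outside figure is needed.

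**Step 2: adult example, general form.** Three units give 3V/W cc/kg at weight W. The rule is met only if 3V/W > 15, that is, only if W < V/5. For any V, every adult of V/5 kg or more is at or below 15 cc/kg. The example covers all weights above 70 kg, so no unit volume makes it fit the rule throughout. This also needs no assumption about V.

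**Step 3: adult example, by assumed unit volume.** At 70 kg the break-even volume is 15 × 70 / 3 = 350 cc per unit.

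| Assumed V (cc) | 3 units (cc) | cc/kg at 70 kg | cc/kg at 80 kg | cc/kg at 100 kg | Rule met only below V/5 (kg) |
|---|---|---|---|---|---|
| 200 | 600 | 8.6 | 7.5 | 6.0 | 40 |
| 250 | 750 | 10.7 | 9.4 | 7.5 | 50 |
| 300 | 900 | 12.9 | 11.3 | 9.0 | 60 |
| 350 | 1050 | 15.0 | 13.1 | 10.5 | 70 |
| 400 | 1200 | 17.1 | 15.0 | 12.0 | 80 |
| 450 | 1350 | 19.3 | 16.9 | 13.5 | 90 |
| 500 | 1500 | 21.4 | 18.8 | 15.0 | 100 |

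At 350 cc or less, 3 units never exceed 15 cc/kg in any adult above 70 kg. At 400, 450 and 500 cc the example agrees with the rule for lighter adults and fails from 80, 90 and 100 kg upward.

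**Step 4: is the boundary sign the whole problem?** As a test only, read the limit as 15 cc/kg or more. The child example is then met exactly. The adult example still fails at every weight above 70 kg if V is 350 cc or less, and above V/5 kg otherwise. Changing the sign would not by itself reconcile both examples.

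**The case against.** The strongest reply is that this is a small wording point. Much of that reply stands, and it limits what may be concluded.

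- **The child conflict is a tie.** Only a patient at exactly 15.0 cc/kg is affected; at 20 kg, any volume above 300 cc is excluded on either reading. This stands.
- **The adult result depends on unit volume.** A reader might infer that the adult example fails outright. The documents do not support that: they give no unit volume, and above 350 cc the example satisfies the rule for some adults. What needs no assumption is that it cannot fit all the weights it covers.
- **Falling outside 2a admits nobody.** A reader might infer that the rule lets a bleeding patient in. Criteria 1 (hemodynamic instability), 2b (bleeding site) and 7 (serious disease or comorbidity in the investigator's judgment) may still exclude. Section 1.6.1 advises against defibrotide in active bleeding without any volume limit. Section 5.2.1.1 calls for discontinuation if bleeding develops on the drug, and Section 5.2.1.2 requires stopping rescue for clinically significant bleeding.
- **2a is not the only numerical bleeding limit.** Section 5.2.1.2 also sets a severity grade for restarting rescue. 2a is the only limit expressed as a volume.
- **No effect on the bleeding comparison is shown.** A reader might infer that between-arm bleeding results depend on which reading a site used. Adverse events are graded by CTCAE, and the bleeding events of special interest come from preferred-term lists (SAP Sections 11.2 and 11.2.1, Appendix I). The entry criterion applies to both arms, and the Prophylaxis Phase ends the day before rescue starts (SAP Section 8.3).

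The reply does not remove the contradiction. That the cases are only examples is no defense when they do not satisfy the rule. The other bleeding provisions do not settle which reading of 2a applies; the rescue stopping rule uses the term clinically significant bleeding without defining it there.

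**Conclusion.** The point holds as an internal contradiction in an eligibility threshold, used at entry and again for rescue. Two parts rest on the documents alone: the child example equals and does not exceed the limit, and the adult example is at or below 15 cc/kg for every adult of V/5 kg or more, whatever the unit volume. One part is conditional: the adult example fails for everyone above 70 kg only if a unit is 350 cc or less.

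For the child the gap is zero, a boundary tie. For adults it can be more than a tie: over an assumed 250 to 350 cc per unit, 3 units at 100 kg give 7.5 to 10.5 cc/kg against a limit of 15. The documents give no count of candidates who would fall between the two readings, so the number affected cannot be estimated. The consequence supported is inconsistent application of 2a between sites, not admission of all such patients and not a distorted safety comparison. It is worth correcting because it bears on patient safety and the correction is cheap.

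**What to change.** Reconcile the threshold and both examples in Protocol Section 4.2, criterion 2a, and in the synopsis, so that each example satisfies the rule as worded. The text should state whether the boundary value counts, and how units relate to cc/kg at a given weight. Carry the single reconciled rule into Section 5.2.1.2, so that entry and rescue use the same criterion. Which threshold is right is for the sponsor; this point takes no view.

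The cost is one line in Section 4.2 and the synopsis at the next amendment, a check of the cross-reference in Section 5.2.1.2, and a memo to sites. The design, sample size and analyses are unaffected.

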## 5 STUDY TREATMENT

### 5.1 Description of Treatment

#### 5.1.1 Study Drug

Defibrotide (defibrotide sodium) is a clear light yellow to brown solution supplied as 200 mg/2.5 mL (concentration of 80 mg/mL) in single-patient-use clear, glass vials. After dilution with 0.9% sodium chloride or 5% dextrose in water (D5W), the final solution should be free of particulates and turbidity.

Excipients include sodium citrate dihydrate, hydrochloric acid and sodium hydroxide (for pH adjustment), and water for injection.

#### 5.1.2 Reference Therapy

The reference therapy in this study is BSC according to institutional guidelines and patient need, excluding defibrotide (see [Section 5.7](#)).

### 5.2 Treatments Administered

Patients will be randomly assigned in a 1:1 ratio to receive defibrotide prophylaxis 25 mg/kg/day or BSC.

#### 5.2.1 Defibrotide Administration

Defibrotide solution is administered intravenously by study site personnel at a dose of 25 mg/kg/day, divided into 4 equal doses of 6.25 mg/kg/dose given as 2-hour infusions every 6 hours. Each dose (infused over a 2 hour  $\pm$ 15 min infusion period) may be administered within  $\pm$ 1 hour of the scheduled dosing time provided that there is at least a 2-hour window between the end of an infusion and the start of the next infusion. Individual doses of defibrotide are determined for individual patients based on body weight at baseline (i.e., the day before conditioning begins for the DP arm, and on the day that conditioning begins for patients in the BSC arm who develop VOD and subsequently receive defibrotide). For the DP arm, 2-4 doses of defibrotide must be administered within 24 hours prior to conditioning. Each of the 4 divided doses per day will be rounded to the nearest 10 mg for adults ( $>35$  kg) and the nearest 5 mg for children ( $\leq 35$  kg) to facilitate efficient drug administration.

After dilution, with D5W or 0.9% sodium chloride, the final concentration of defibrotide for administration should be in the range of 4 to 20 mg/mL, as appropriate for infusion over 2 hours. Detailed procedures for preparation of study drug will be provided separately.

Defibrotide (JZP-381)  
Clinical Trial Protocol: 15-007 Version 4.0

Jazz Pharmaceuticals, Inc.  
20 August 2018

Defibrotide may be held for surgical procedures or to accommodate other urgent medication delivery without necessitating dose modification. For surgical procedures, it is recommended that defibrotide administration be completed more than 2 hours prior to intervention. Scheduling may also be adjusted to accommodate other medications and interventions, such as dialysis. While the intent is to treat every 6 hours, the schedule may be adjusted without rendering the patient ineligible or causing protocol violation as long as the daily dose does not alter substantially.

#### 5.2.1.1 Defibrotide Prophylaxis

For patients randomized to receive defibrotide prophylaxis, 2-4 doses of defibrotide should be administered within 24 hours before the first dose of conditioning regimen. Defibrotide administration is recommended for a minimum of 21 days and ending no later than Day +30 post-HSCT. Patients in this arm of the study will also receive standard of care therapy based on institutional guidelines and patient need (i.e., BSC). Patients must undergo Day +15 post-HSCT assessments before hospital discharge. If a patient is discontinued early from study/study treatment (prior to Day +15 post-HSCT), the Day +15 post-HSCT assessments must be completed on the day of study/study treatment discontinuation (+1 day).

If a patient on defibrotide develops bleeding, defibrotide should be discontinued. Additionally, temporary discontinuation of defibrotide is recommended for patients at significant risk of major bleeding who are receiving defibrotide (prophylactically or as rescue medication) and who undergo surgery or invasive procedures (see [Section 1.6.1](#)).

#### 5.2.1.2 Defibrotide Rescue Treatment for Patients who Develop VOD

For patients who develop VOD per modified Seattle criteria in either the DP or BSC arms, defibrotide will be administered as treatment for VOD until resolution of VOD or hospital discharge, whichever is sooner, and may continue beyond Day +30 post-HSCT. Patients must be hemodynamically stable and not at risk of bleeding, as defined in the first 3 exclusion criteria (#1, #2, #3) listed in [Section 4.2](#), to receive defibrotide as rescue treatment for VOD. Patients with VOD undergoing rescue treatment with defibrotide will continue to receive individualized standard of care therapy (BSC) based on local institutional guidelines and patient need. Medications that increase risk of bleeding must be stopped 24 hours prior to the start of defibrotide rescue treatment (see [Section 5.7.6](#)).

Defibrotide administration must be stopped if a patient has clinically significant bleeding. Defibrotide may be re-initiated if the bleeding is controlled and is of severity  $\leq$  grade 1.

The daily dose of defibrotide in patients who receive rescue treatment with defibrotide after being randomized to the DP or BSC arm will be based on body weight at baseline (i.e., within 24 hours before conditioning begins for the DP arm, and on the day that conditioning begins for patients in the BSC arm who develop VOD and subsequently receive defibrotide).

Defibrotide (JZP-381)  
Clinical Trial Protocol: 15-007 Version 4.0

Jazz Pharmaceuticals, Inc.  
20 August 2018

---

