The safety of defibrotide 25 mg/kg/day as prophylaxis has been demonstrated in children undergoing myeloablative conditioning considered to be at high risk of developing VOD (Corbacioglu et al. 2012). Incidences of AEs, serious adverse events (SAEs), and events leading to discontinuation were similar between the defibrotide and control groups (207 SAEs in 108 patients in the defibrotide group and 231 SAEs in 103 patients in the control group). Although the most common AE considered by the investigator to be related to defibrotide was hemorrhage, the cumulative incidence of hemorrhage was similar between groups (39 [22%] of 177 patients in the defibrotide group vs 37 [21%] of 176 patients in the control group;  $p=0.8176$ ). Overall, most fatal AEs were either neoplasms (12 [7%] of 177 patients in the defibrotide group and 14 [8%] of 176 patients in the control group) or infections (6 [3%] patients in the defibrotide group and 11 [6%] patients in the control group). In the intent-to-treat (ITT) population, patients who underwent allogeneic HSCT and who received defibrotide prophylaxis had a lower overall incidence of acute graft-versus-host disease (GvHD) (all grades) by Day +30 and +100 post-HSCT compared with those in the control group (Day +30 post-HSCT, 34% vs 53%  $p=0.004$ ; Day +100 post-HSCT, 47% vs 67%  $p=0.002$ ). A lower incidence of acute GvHD was also observed when grade 1 toxicity was excluded.

Defibrotide (JZP-381)  
Clinical Trial Protocol: 15-007 Version 4.0

Jazz Pharmaceuticals, Inc.  
20 August 2018

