### 1.6.1 Hemorrhage

Defibrotide increased the activity of fibrinolytic enzymes in vitro and may increase the risk of bleeding in patients with VOD after HSCT. Defibrotide should not be used in patients with active bleeding. If a patient on defibrotide develops bleeding, defibrotide should be discontinued. Additionally, temporary discontinuation of defibrotide is recommended for patients at significant risk of major bleeding who undergo surgery or invasive procedures.

Concomitant use of defibrotide and a systemic anticoagulant or fibrinolytic therapy may increase the risk of bleeding. Therefore, anticoagulants and fibrinolytic agents should be discontinued prior to defibrotide treatment and the start of defibrotide administration should be delayed until the effects of the anticoagulant have abated. However, in this study, anticoagulant fibrinolytic therapy for routine central venous line management and intermittent dialysis or ultrafiltration is permitted, fibrinolytic instillation for central venous line occlusion is also permitted, and heparin use is allowed in both treatment arms (up to a maximum of 100 U/kg/day).

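### The protocol does not say which of two bleeding rules governs rescue defibrotide, or whether prophylaxis may resume after a bleed

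*Protocol*

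**What the plan says.** **General risk text (Protocol 1.6.1).** "Defibrotide should not be used in patients with active bleeding. If a patient on defibrotide develops bleeding, defibrotide should be discontinued". The section sets no severity threshold and has no restart provision after a bleed. It is not limited to one phase of treatment, and it describes the risk in patients who have VOD after transplant.

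**Prophylaxis (Protocol 5.2.1.1).** The stop instruction is repeated word for word: "If a patient on defibrotide develops bleeding, defibrotide should be discontinued". The next sentence recommends a temporary discontinuation around procedures for patients at significant risk of major bleeding. It covers patients "receiving defibrotide (prophylactically or as rescue medication) and who undergo surgery or invasive procedures" and cites Section 1.6.1.

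**Rescue (Protocol 5.2.1.2).** "Defibrotide administration must be stopped if a patient has clinically significant bleeding". Then: "Defibrotide may be re-initiated if the bleeding is controlled and is of severity" grade 1 or less. The stop sentence cites no definition of clinically significant bleeding. The only definition is in exclusion criterion 2 of Section 4.2 ("Patient has acute bleeding that is clinically significant within 24 hours before the start of study treatment"), which 5.2.1.2 invokes as a condition for receiving rescue.

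The SAP summarises exposure, treatment discontinuation and bleeding events (Sections 9.2.2, 9.2.3, 11.1, 11.2 and 11.2.1). It contains no rule that settles the point.

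**The concern.** A patient on rescue defibrotide falls under both 1.6.1 and 5.2.1.2. If that patient has a minor bleed, 1.6.1 advises discontinuing, while 5.2.1.2 does not require it. If the drug is stopped and the bleed subsides to grade 1, 5.2.1.2 permits dosing again and 1.6.1 offers no such route. In prophylaxis the trigger is clear, but a site cannot tell whether a bleed ends dosing for good.

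Bleeding is the first risk listed in Protocol 1.6, and Section 1.3 reports that haemorrhage was the most common event considered related to defibrotide in the earlier trial. With about 100 sites planned, different readings would leave similar patients on or off drug. That matters for their safety. It also matters for three summaries: rescue exposure, reasons for stopping, and adverse events leading to discontinuation of study drug.

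**Working it through.** No stated figure rests on this text, so the check is a comparison of the sections, followed by a rough scale.

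**Comparison**

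| Question | 1.6.1 (any patient on defibrotide) | 5.2.1.1 (prophylaxis) | 5.2.1.2 (rescue) |
|---|---|---|---|
| What triggers stopping? | Bleeding, unqualified | Same sentence | Clinically significant bleeding |
| Force of the instruction | Should | Should | Must |
| May dosing resume after a bleed? | Not stated | Not stated | Yes, if controlled and grade 1 or less |
| Use while bleeding is active | Advised against | Not stated | Not addressed as such |

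1. *Trigger, rescue.* 1.6.1 and 5.2.1.2 differ for bleeding below the clinically significant level. One advises stopping; the other says nothing about it.
2. *Resumption, rescue.* 5.2.1.2 has a restart path and 1.6.1 has none.
3. *Active bleeding.* 1.6.1 states: "Defibrotide should not be used in patients with active bleeding". Protocol Table 6 describes grade 1 as a mild event that is still present. The protocol does not say whether controlled grade 1 bleeding counts as active, so the two sections may or may not collide here.
4. *Trigger, prophylaxis.* 1.6.1 and 5.2.1.1 agree.
5. *Resumption, prophylaxis.* Neither section addresses it. Because 5.2.1.1 uses the word temporary for procedures and omits it for bleeding, a reader could take the bleeding stop as permanent. The text does not say so.

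**Rough scale**

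Protocol 1.3 gives "39 [22%] of 177 patients in the defibrotide group" and 37 of 176 controls with haemorrhage (p = 0.8176): 39/177 = 22.0% and 37/176 = 21.0%. These are cumulative incidences from a paediatric trial, with no breakdown by severity or by whether the patient was on drug.

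- Prophylaxis: 0.22 × 200 = 44 DP patients who might meet the unstated resumption rule.
- Rescue: Protocol 9.3 plans for 14% and 28% with VOD or death by Day +30, so 0.14 × 200 + 0.28 × 200 = 28 + 56 = 84 events. Its simulated average is 68. Assuming the same 22%, 0.22 × 68 = 15.0 and 0.22 × 84 = 18.5, or roughly 15 to 18 patients with any haemorrhage.

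The rescue range treats deaths as if they were rescued patients. It leaves out VOD after Day +30 and rescues that the adjudication committee does not confirm. It is illustrative only.

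**The case against.** The strongest reply is that the rules are phase-specific: 5.2.1.1 is headed prophylaxis, 5.2.1.2 is headed rescue, and 1.6.1 is background in the Introduction, over which an operative dosing section would normally prevail. That is a sensible reading, but the protocol does not state it. Section 1.6.1 is unrestricted and refers to patients with VOD, and 5.2.1.1 points to it in a sentence that expressly covers rescue use.

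Other parts of the reply stand, and they rule out four stronger readings that a reader might infer.

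- *That rescue is stopped only for clinically significant bleeding, so the sections give opposite orders.* Section 5.2.1.2 does not say only, and it does not tell sites to continue through lesser bleeding. A site that stops at any bleed complies with both sections.
- *That 5.2.1.2 plainly allows dosing during a bleed.* The restart requires the bleeding to be controlled as well as grade 1 or less.
- *That about 44 DP patients face conflicting stop rules.* They fall where 1.6.1 and 5.2.1.1 agree. What they lack is a statement on resumption.
- *That the conflict changes the treatment being tested or biases the primary result.* The divergent rule applies after an investigator diagnosis of VOD. For patients whose VOD the adjudication committee has confirmed by then, the primary event has already occurred. BSC patients rescued without confirmation are censored at rescue initiation (Protocol 9.8.1, SAP 10.1). Safety is summarised separately for the prophylaxis and rescue phases (SAP 8.3). DP patients rescued without confirmation do stay in follow-up, but the documents give nothing from which an effect through them could be derived.

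**Conclusion.** The inconsistency is real and can be verified from three sections. During rescue, the protocol does not settle whether lesser bleeding calls for stopping, or whether the restart provision holds against 1.6.1. During prophylaxis, the stop trigger is consistent and only resumption is left open. On every reading, clinically significant bleeding stops the drug, so the uncertainty is confined to lesser bleeding in rescue and to restarting in either phase.

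The number affected cannot be derived from the documents. The figures of about 44 (prophylaxis, resumption) and about 15 to 18 (rescue, any haemorrhage) rest on carrying a paediatric rate of 22% into a mixed adult and paediatric trial. They also rest on ignoring severity and timing, and for rescue on using planned events as a stand-in for rescued patients. Since controls in the earlier trial had 21%, the rate should not be read as bleeding caused by the drug.

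The point should be fixed because it concerns a safety stopping rule and the comparability of rescue exposure and discontinuation counts across sites. It is not grounds for doubting the primary comparison.

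**What to change.** Reconcile Protocol Sections 1.6.1, 5.2.1.1 and 5.2.1.2 so that, for prophylaxis and for rescue, each states consistently what bleeding triggers stopping and whether dosing may resume. Different rules for the two phases are acceptable if the text says they differ by phase and 1.6.1 refers to them. The same edit should say what clinically significant means in the stop sentence of 5.2.1.2, and how controlled grade 1 bleeding relates to the active-bleeding statement in 1.6.1. Which clinical rule applies is for the sponsor and its clinical advisers; none is proposed here.

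The cost is protocol wording, issued as an amendment with a note to sites. The sample size, the interim design and the SAP analyses do not change.
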